5.3 Flowchart of the study cohort assembly

For dabigatran 150mg vs. warfarin

	Optum		Truven		Medicare	
	Less Excluded Patients	Remaining Patients	Less Excluded Patients	Remaining Patients	Less Excluded Patients	Remaining Patients
All patients		77,673,639		200,203,908		6,886,908
Did not meet cohort entry criteria	76,847,731	825,908	199,014,982	1,188,926	-2,335,930	4,550,978

Excluded due to insufficient enrollment	-80,642	745,266	-107,905	1,081,021	-1,565,261	2,985,717
Excluded due to prior use of referent	-564,968	180,298	-751,832	329,189	-2,241,426	744,291
Excluded due to prior use of exposure	-44,640	135,658	-71,891	257,298	-196,688	547,603
Excluded because patient qualified in >1 exposure category	-5	135,653	-9	257,289	-24	547,579
Excluded based on Dabigatran (dose other than 150mg)	-306	135,347	-534	256,755	-2,557	545,022
Excluded based on Age	0	135,347	0	256,755	-162	544,860
Excluded based on Gender	0	135,347	0	256,755	0	544,860
Excluded based on Inclusion 1a or 1b or 1 c - Atrial fibrillation	-71,189	64,158	-135,349	121,406	-220,602	324,258
Excluded based on Inclusion 2a-2e History of Stroke, TIA, Systemic embolism / EF<40% / NYHA 2 or higher / Age >75 / Age 65+RF	-11,313	52,845	-17,737	103,669	-24,940	299,318
Excluded based on Inclusion 3 - Age >= 18	-1	52,844	-1	103,668	0	299,318
Excluded based on Exclusion 1 - History of heart valve disorders	-17,688	35,156	-5,687	97,981	-94,948	204,370
Excluded based on Exclusion 2a - Severe/disabling stroke	-576	34,580	-1,111	96,870	-3,090	201,280
Excluded based on Exclusion 2b - Any stroke	-960	33,620	-1,391	95,479	-3,948	197,332
Excluded based on Exclusion 3a - Major Surgery	-1,091	32,529	-2,526	92,953	-6,491	190,841
Excluded based on Exclusion 3c - Intracranial hemorrhage - Inpatient	-51	32,478	-331	92,622	-595	190,246
Excluded based on Exclusion 3d - Gastrointestinal hemorrhage	-4,848	27,630	-1,601	91,021	-5,353	184,893
Excluded based on Exclusion 3e - Symptomatic or endoscopically documented gastroduodenal ulcer disease	-121	27,509	-714	90,307	-3,148	181,745
Excluded based on Exclusion 3f - Hemorrhagic disorder or bleeding diathesis	-257	27,252	-756	89,551	-1,787	179,958
Excluded based on Exclusion 3i - Uncontrolled hypertension	-51	27,201	-400	89,151	-804	179,154

Excluded based on Exclusion 7 - Severe renal impairment	-1,301	25,900	-4,674	84,477	-12,016	167,138
Excluded based on Exclusion 8 & 9 - Active infective endocarditis and liver disease	-36	25,864	-255	84,222	-616	166,522

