Excluded based on Exclusion 10 & 11 - Pregnancy & Anemia and Thrombocytopenia	-191	25,673	-1,229	82,993	-2,798	163,724
Excluded based on Exclusion 14 - Alcohol abuse or dependence	-28	25,645	-103	82,890	-138	163,586
Excluded based on Exclusion 14 - Drug abuse or dependence	-22	25,623	-47	82,843	-111	163,475
Excluded based on Exclusion 14 - CCI (180 days)	-7	25,616	-47	82,796	-1,939	161,536
Final cohort		25,616		82,796		161,536

* Medicare database includes all patients using a novel oral anticoagulant and a subset of patients using warfarin during 2011-2017.

6. Variables

6.1 Exposure-related variables:

Study drug:

The study exposure of interest is initiation of dabigatran. Initiation will be defined by no use of dabigatran or a comparator in the prior 6 months before treatment initiation (washout period).

Comparator agents-

- Initiators of dabigatran (150mg) will be compared to initiators of-
 - Warfarin

6.2 Covariates:

- Age
- Sex
- Combined Comorbidity Index (CCI), measured over the baseline covariate assessment period, defined as 180 days prior to and including index date

Covariates listed above represent only a small subset of covariates that will ultimately be controlled for in the design and analysis. We use the covariates above only for initial feasibility analyses to judge whether there is likely to be sufficient overlap between treatment groups to proceed with the study. Remaining covariates are defined only after the study has passed the initial feasibility analysis and the initial power assessment and are listed in Table 1 (**Appendix B**).

6.3 Outcome variables and study follow-up:

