1c	
• There is documentation of symptomatic or asymptomatic paroxysmal or persistent AF on 2 separate occasions, at least 1 day apart, one of which is within 6 m before randomization.
 
In this case, AF may be documented by 12 lead ECG, rhythm strip, pacemaker/ICD electrogram, or Holter ECG. The duration of AF should be at least 30 s.
 
Electrograms (not marker channels or mode switch episodes) from pacemakers and defibrillators can be used to document only 1 episode of paroxysmal or persistent AF
	
>2 Diagnoses separated by 1 day to 30 days, measured 12 months prior to and including day of drug initiation in any diagnosis position and inpatient or outpatient care setting
 
Atrial fibrillation ICD-9 diagnosis: 427.31 ICD-10 diagnosis: I48.0x, I48.1x, I48.2x, I48.9x
		
2	In addition to documented AF, patients must have one of the following: (2a or 2b or 2c or 2d or 2e)			
2a	• History of previous stroke, TIA, or systemic embolism	
Measured any time prior to and including day of drug initiation in any diagnosis position and inpatient care setting
 
Any stroke ICD-9 diagnosis: 430.xx, 431.xx, 433.xx, 434.xx, 436.xx
 
Systemic embolism ICD-9 diagnosis: 444.xx (arterial embolism) ICD-10 diagnosis: 174.x arterial embolism and thrombosis
 
TIA ICD-9 diagnosis: 435.xx (Transient cerebral ischemia)
		
2b	• Ejection fraction <40% documented by echocardiogram, radionuclide or contrast angiogram in the last 6 m	
Measured 180 days prior to and including day of drug initiation in any diagnosis position and inpatient care setting
 
Heart failure, systolic ICD-9 diagnosis: 428.2x, 428.4x ICD-10 diagnosis: I50.2x, I50.4x
		
2c	• Symptomatic heart failure, New York Heart Association class 2 or higher in the last 6 m	
Measured 180 days prior to and including day of drug initiation in any diagnosis position and inpatient care setting
 
Congestive heart failure ICD-9 diagnosis: 428.x, 398.91, 402.01, 402.11, 402.91, 404.01, 404.11, 404.91, 404.03, 404.13, 404.93 ICD-10 diagnosis: I50.1, I50.2x, I50.3x, I50.4x, I50.8x, I50.9, I09.81, I11.0, I13.0, I13.2
		
2d	• Age ≥75 y	
Measured on the day of drug initiation
 
Age ≥75
		

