...median [IQR]	4.30 [4.10, 4.60]	4.40 [4.10, 4.60]	-0.23	4.30 [4.10, 4.60]	4.40 [4.15, 4.60]	-0.25	N/A	N/A	#VALUE!	4.30 (0.44)	4.40 (0.43)	-0.23
...Missing; n (%)	18,055 (79.7%)	2,225 (75.8%)	0.09	67,238 (99.2%)	14,765 (98.9%)	0.03	N/A	N/A	#VALUE!	85,293 (94.3%)	16,990 (95.1%)	-0.04
Comorbidity Scores												
CCI (180 days)-ICD9 and ICD10 v2												
...mean (sd)	2.62 (1.44)	2.62 (1.34)	0.00	2.78 (1.68)	2.79 (1.56)	-0.01	1.42 (1.41)	1.32 (1.38)	0.07	1.95 (1.50)	1.92 (1.44)	0.02
...median [IQR]	2.00 [2.00, 3.00]	2.00 [2.00, 3.00]	0.00	2.00 [2.00, 4.00]	2.00 [2.00, 4.00]	0.00	1.00 [0.00, 2.00]	1.00 [0.00, 2.00]	0.00	1.40 (1.50)	1.41 (1.44)	-0.01
Non-Frailty; n (%)	12,577 (55.5%)	1,612 (54.9%)	0.01	33,237 (49.0%)	7,284 (48.8%)	0.00	3,400 (2.5%)	524 (2.1%)	0.03	49,214 (21.7%)	9,420 (21.9%)	0.00
Frailty Score (mean): Empirical Version 365 days, v2												
...mean (sd)	0.17 (0.04)	0.17 (0.04)	0.00	0.18 (0.05)	0.17 (0.05)	0.20	12.15 (9.76)	10.54 (9.32)	0.17	7.37 (7.56)	6.24 (7.13)	0.15
...median [IQR]	0.16 [0.14, 0.19]	0.16 [0.14, 0.19]	0.00	0.17 [0.15, 0.21]	0.16 [0.14, 0.19]	0.20	10.13 [5.57, 16.45]	8.75 [4.29, 14.71]	0.14	6.15 (7.56)	5.19 (7.13)	0.13
Healthcare Utilization												
Any hospitalization; n (%)	0 (0.0%)	0 (0.0%)	#DIV/0!	17,074 (25.2%)	4,804 (32.2%)	-0.16	19,589 (14.1%)	4,815 (19.1%)	-0.13	36,663 (16.2%)	9,619 (22.3%)	-0.16
Any hospitalization within prior 30 days; n (%)	0 (0.0%)	0 (0.0%)	#DIV/0!	9,626 (14.2%)	3,296 (22.1%)	-0.21	11,829 (8.7%)	2,910 (11.5%)	-0.09	21455 (9.5%)	6206 (14.4%)	-0.15
Any hospitalization during prior 31-180 days; n (%)	0 (0.0%)	0 (0.0%)	#DIV/0!	8,232 (12.1%)	1,717 (11.5%)	0.02	8,606 (6.3%)	2,082 (8.3%)	-0.08	16838 (7.4%)	3799 (8.8%)	-0.05
Endocrinologist Visit; n (%)	436 (1.9%)	84 (2.9%)	-0.07	1,932 (2.8%)	501 (3.4%)	-0.03	4,050 (3.0%)	874 (3.5%)	-0.03	6418 (2.8%)	1459 (3.4%)	-0.03
Endocrinologist Visit (30 days prior); n (%)	139 (0.6%)	21 (0.7%)	-0.01	633 (0.9%)	176 (1.2%)	-0.03	1,150 (0.8%)	276 (1.1%)	-0.03	1922 (0.8%)	473 (1.1%)	-0.03
Endocrinologist Visit (31 to 180 days prior); n (%)	381 (1.7%)	72 (2.5%)	-0.06	1,650 (2.4%)	413 (2.8%)	-0.03	3,536 (2.6%)	755 (3.0%)	-0.02	5567 (2.5%)	1240 (2.9%)	-0.02
Internal medicine/family medicine visits; n (%)	19,784 (87.3%)	2,435 (82.9%)	0.12	52,971 (78.1%)	11,827 (79.2%)	-0.03	108,913 (80.0%)	20,381 (80.8%)	-0.02	181668 (80.2%)	34643 (80.4%)	-0.01

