Internal medicine/family medicine visits (30 days prior); n (%)	13,564 (59.8%)	1,529 (52.1%)	0.16	33,572 (49.5%)	7,777 (52.1%)	-0.05	68,566 (50.4%)	12,510 (49.6%)	0.02	115702 (51.1%)	21816 (50.6%)	0.01
Internal medicine/family medicine visits (31 to 180 days prior); n (%)	17,797 (78.5%)	2,119 (72.2%)	0.15	48,286 (71.2%)	10,294 (69.0%)	0.05	95,817 (70.4%)	17,389 (68.9%)	0.03	161900 (71.5%)	29802 (69.2%)	0.05
Cardiologist visit; n (%)	11,235 (49.6%)	1,976 (67.3%)	-0.37	35,004 (51.6%)	9,003 (60.3%)	-0.18	85,057 (62.5%)	19,330 (76.6%)	-0.31	131296 (58.0%)	30309 (70.3%)	-0.26
Number of Cardiologist visits (30 days prior); n (%)	6,801 (30.0%)	1,379 (47.0%)	-0.35	20,128 (29.7%)	6,908 (46.3%)	-0.35	53,448 (39.3%)	14,249 (56.5%)	-0.35	80377 (35.5%)	22536 (52.3%)	-0.34
Number of Cardiologist visits (31 to 180 days prior); n (%)	8,195 (36.2%)	1,255 (42.7%)	-0.13	27,617 (40.7%)	5,842 (39.1%)	0.03	61,773 (45.4%)	12,141 (48.1%)	-0.05	97585 (43.1%)	19238 (44.6%)	-0.03
Electrocardiogram v2; n (%)	11,225 (49.5%)	2,064 (70.3%)	-0.43	39,015 (57.6%)	11,173 (74.8%)	-0.37	77,673 (57.1%)	19,434 (77.0%)	-0.43	127913 (56.5%)	32671 (75.8%)	-0.42
Use of glucose test strips; n (%)	176 (0.8%)	33 (1.1%)	-0.03	475 (0.7%)	113 (0.8%)	-0.01	1,262 (0.9%)	261 (1.0%)	-0.01	1913 (0.8%)	407 (0.9%)	-0.01
Dialysis; n (%)	4 (0.0%)	0 (0.0%)	#DIV/0!	0 (0.0%)	0 (0.0%)	#DIV/0!		**	0 (0.0%)	#VALUE!	#VALUE!	#VALUE!
number of different/distinct medication prescriptions												
...mean (sd)	7.72 (3.82)	8.13 (4.07)	-0.10	9.26 (4.52)	9.27 (4.58)	0.00	8.30 (3.85)	8.59 (4.06)	-0.07	8.53 (4.06)	8.79 (4.25)	0.00
...median [IQR]	7.00 [5.00, 10.00]	8.00 [5.00, 10.00]	-0.25	9.00 [6.00, 12.00]	9.00 [6.00, 12.00]	0.00	8.00 [6.00, 10.00]	8.00 [6.00, 11.00]	0.00	5.79 (4.76)	6.43 (4.80)	0.00
Number of Hospitalizations												
...mean (sd)	0.00 (0.00)	0.00 (0.00)	#DIV/0!	0.28 (0.51)	0.35 (0.55)	-0.13	0.16 (0.43)	0.21 (0.47)	-0.11	0.18 (0.43)	0.24 (0.48)	0.00
...median [IQR]	0.00 [0.00, 0.00]	0.00 [0.00, 0.00]	#DIV/0!	0.00 [0.00, 1.00]	0.00 [0.00, 1.00]	0.00	0.00 [0.00, 0.00]	0.00 [0.00, 0.00]	0.00	0.00 (0.52)	0.00 (0.55)	0.00
Number of hospital days												
...mean (sd)	0.00 (0.11)	0.00 (0.00)	0.00	1.61 (4.76)	1.50 (3.28)	0.03	0.80 (2.85)	0.85 (2.46)	-0.02	0.96 (3.41)	1.02 (2.70)	0.00
...median [IQR]	0.00 [0.00, 0.00]	0.00 [0.00, 0.00]	0.00	0.00 [0.00, 1.00]	0.00 [0.00, 2.00]	0.00	0.00 [0.00, 0.00]	0.00 [0.00, 0.00]	0.00	0.00 (4.30)	0.00 (3.14)	0.00
Number of Emergency Department (ED) visits v3												

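### Table 1 shows no prior hospitalization in any of 25,601 Optum patients, against 26.4% in MarketScan and 15.1% in Medicare; the cause should be traced and corrected before the comparative run

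*Combined protocol and SAP*

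**What the plan says.** Appendix B, Table 1, has three prior-admission rows under healthcare utilization: "Any hospitalization; n", "Any hospitalization within prior 30 days; n" and "Any hospitalization during prior 31-180 days; n". All three print 0 (0.0%) in both Optum arms, in the unmatched and the matched table. The mean number of hospitalizations in Optum is 0.00 (SD 0.00). For any hospitalization, the unmatched table gives (warfarin / dabigatran) 25.2% / 32.2% in MarketScan, 14.1% / 19.1% in Medicare and 16.2% / 22.3% pooled. The 30-day and 31-to-180-day rows together fix the window at 180 days. That agrees with the baseline period in Section 6.2, "defined as 180 days prior to and including index date".

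Section 5.2.2, the Section 5.3 flowchart and Appendix A apply one list of criteria to all three databases. None of them excludes a patient for a recent admission, and no text explains the Optum zeros. Several criteria rely on inpatient claims. Inclusion routes 2b and 2c (heart failure) carry the definition "Measured 180 days prior to and including day of drug initiation in any diagnosis position and inpatient care setting". The flowchart row "Excluded based on Exclusion 2b - Any stroke" corresponds in Appendix A to an inpatient primary diagnosis in the 14 days up to index. Section 9 puts every covariate except laboratory values into the propensity score.

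**The concern.** A population starting anticoagulation for atrial fibrillation, drawn under the same rules as two other claims databases, should include some patients with an admission in the previous six months. Zero in more than 25,000 points to a fault in how the Optum cohort or its covariates were built.

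The two possible faults have different consequences:

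- **Cohort fault.** If hospitalized patients were removed, Optum follows an entry rule that the protocol does not state, and the pooled result combines differently selected populations as if they were one. In that case nobody in the final Optum cohort can have qualified through inclusion routes 2b or 2c.
- **Covariate fault.** If the patients are present but the variables are empty, hospitalization is a constant in the Optum propensity score. The 0 versus 0 after matching then looks like balance but carries no information. Elsewhere the variable separates the arms before matching: within 30 days it is 14.2% versus 22.1% in MarketScan (standardized difference -0.21).

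**Working it through.** **Inputs.** Unmatched arm sizes and hospitalization counts come from Appendix B, Table 1; exclusion counts from Section 5.3; outcome risk from Section 9; matched numbers, expected events and power from Section 10.

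**1. Reproduce the printed percentages (any hospitalization, unmatched).**

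| Source | Warfarin | Dabigatran | Both arms |
|---|---|---|---|
| Optum | 0/22,665 = 0.0% | 0/2,936 = 0.0% | 0/25,601 = 0.0% |
| MarketScan | 17,074/67,790 = 25.2% | 4,804/14,929 = 32.2% | 21,878/82,719 = 26.4% |
| Medicare | 19,589/136,087 = 14.4% | 4,815/25,230 = 19.1% | 24,404/161,317 = 15.1% |
| Pooled | 36,663/226,542 = 16.2% | 9,619/43,095 = 22.3% | |

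All agree with the table except Medicare warfarin, printed as 14.1%; that slip does not affect the argument. Without the Optum zeros the pooled row would read 36,663/203,877 = 18.0% and 9,619/40,159 = 24.0%.

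**2. Chance.** At the Medicare rate, the probability of no admission in 25,601 patients is (1 - 0.1513)^25,601, below 10^-1800. At the MarketScan rate it is smaller still.

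**3. Absence of inpatient data.** Exclusion 2b, defined on inpatient claims within 14 days, removed 960 Optum patients. Intracranial hemorrhage, also inpatient-only, removed 51. The primary outcome needs an inpatient primary diagnosis and has an Optum risk of 4.57 per 1,000. If the programs follow Appendix A, Optum has inpatient claims inside the baseline window.

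**4. Where hospitalized patients could have been lost.** The 960 removals show that recently admitted patients were still in the Optum cohort at step 2b. The Optum rows from there subtract exactly, from 33,620 to 25,616, so any later loss sits inside a printed row. One row stands out, "Excluded based on Exclusion 3d - Gastrointestinal hemorrhage":

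- Optum 4,848/32,478 = 14.9%
- MarketScan 1,601/92,622 = 1.7%
- Medicare 5,353/190,246 = 2.8%

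The next largest later Optum row is renal impairment, at 1,301. Covariates often recorded in hospital are also lower in Optum than in MarketScan and Medicare: acute MI 0.8% against 2.6% and 1.4%; previous cardiac procedure 0.10% against 1.06% and 0.65%; pneumonia 2.1% against 6.4% and 3.5%. This leans toward real removal but does not establish it.

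**5. Size under each explanation, borrowing the other databases' rates p.**

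- Covariates empty, patients still present: 25,601 × p = 3,873 (Medicare) to 6,771 (MarketScan) misclassified.
- Patients removed, so missing in addition to the 25,601: 25,601 × p/(1 - p). Medicare: 25,601 × 0.1513/0.8487, about 4,560. MarketScan: 25,601 × 0.2645/0.7355, about 9,210. All Optum rows after 2b together remove 33,620 - 25,616 = 8,004, so the upper end could be reached only if some were also lost earlier.

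**6. Weight of Optum in the pool.** Matched patients: 5,580/78,140 = 7.1%. Expected events: 25.5/440.7 = 5.8%. Power = Φ(√D/2 × |ln HR| - 1.96). With D = 440.7 this reproduces the plan's 0.992 (HR 0.66) and 0.978 (margin 1.46). Without Optum, D = 145.2 + 269.6 = 414.8, giving 0.988 and 0.971.

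**The case against.** The strongest case against is one of proportion. Optum supplies 5.8% of expected events. The plan does not state a pooling method, but with event-proportional weights even a two-fold bias in the Optum hazard ratio would move the pooled one by a factor of 2^0.058 = 1.04. Balance, follow-up and power are already shown by database. This stands, and it sets the severity.

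Three stronger readings are tempting, and the documents do not support them:

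- **That Optum carries an exclusion missing from the protocol.** A listed step that behaves differently in Optum would give the same zeros, and the GI-hemorrhage row is a candidate. That row is a lead and not proof.
- **That recent hospitalization is uncontrolled confounding in Optum.** If hospitalized patients were removed, admission is constant within Optum and cannot confound that contrast. If the covariates failed, the matched Optum arms are still close on comorbidity index, frailty, emergency visits, 30-day cardiologist visits and acute MI, which are partial proxies. Residual confounding is then possible but not shown. The MarketScan gap of 14.2% versus 22.1% is before matching; afterwards it is 22.2% versus 21.5%.
- **That the row "Number of hospital days" proves the variables broken.** Its SD of 0.11 in Optum warfarin, beside zero hospitalizations, implies a sum of squares of about 250 to 300, for example one patient with 16 or 17 days. A stay that began before the window and ran into it could produce that. The documents do not say how such stays are counted, so the evidence is weak.

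The borrowed rates also come from databases with a different payer mix, so the ranges in the working are illustrative.

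**Conclusion.** The discrepancy is certain and its cause is open. Table 1 shows 0 of 25,601 unmatched and 0 of 5,580 matched Optum patients with an admission in 180 days. Chance and absent inpatient data are ruled out, the latter on the assumption that the Optum programs follow the Appendix A definitions. No listed criterion accounts for the zeros.

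If patients were lost, this is a problem of comparability between sources, with roughly 4,600 to 9,200 patients missing. If the covariates are empty, it is a problem of adjustment and uninformative balance, with roughly 3,900 to 6,800 patients misclassified. The two figures belong to incompatible explanations and must not be combined.

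A reader might infer that the primary conclusion is in danger or that Optum must leave the pool now. Neither follows: the power loss without Optum is at most 0.007, and removal is premature while the cause is unknown. This is a validity and comparability issue that should be fixed.

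**What to change.** Before the comparative run (Section 13 records no run date), trace the cause in Optum. Start with the code for the GI-hemorrhage step and the code for the hospitalization variables.

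- If a cohort step removed hospitalized patients, correct it to the Appendix A definition, rerun the Optum flowchart and re-match.
- If the covariates failed, rebuild them from the inpatient claims already used for the outcome, refit the Optum propensity score and re-match.
- In either case reprint Table 1 and the Optum and pooled Section 10 figures, and record the cause in the protocol.
- If the cause is still unresolved at the time of analysis, show the pooled estimate with and without Optum.

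The cost is reprogramming and a rerun in one database, with updated tables. No new data are needed, and the Optum cohort may grow.

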Appendix B

...median [IQR]	0.00 [0.00, 1.00]	1.00 [0.00, 2.00]	-0.59	1.00 [0.00, 2.00]	1.00 [0.00, 2.00]	0.00	1.00 [0.00, 2.00]	1.00 [1.00, 3.00]	0.00	0.60 (1.98)	0.76 (2.19)	0.00
Number of HbA1c tests ordered												
...mean (sd)	0.36 (0.67)	0.39 (0.70)	-0.04	0.14 (0.45)	0.16 (0.48)	-0.04	0.37 (0.69)	0.41 (0.72)	-0.06	0.30 (0.63)	0.32 (0.65)	0.00
...median [IQR]	0.00 [0.00, 1.00]	0.00 [0.00, 1.00]	0.00	0.00 [0.00, 0.00]	0.00 [0.00, 0.00]	0.00	0.00 [0.00, 1.00]	0.00 [0.00, 1.00]	0.00	0.00 (0.67)	0.00 (0.69)	0.00
Number of glucose tests ordered												
...mean (sd)	0.11 (0.90)	0.16 (0.94)	-0.05	0.10 (0.54)	0.11 (0.58)	-0.02	0.11 (0.52)	0.13 (0.49)	-0.04	0.11 (0.58)	0.13 (0.56)	0.00
...median [IQR]	0.00 [0.00, 0.00]	0.00 [0.00, 0.00]	0.00	0.00 [0.00, 0.00]	0.00 [0.00, 0.00]	0.00	0.00 [0.00, 0.00]	0.00 [0.00, 0.00]	0.00	0.00 (0.65)	0.00 (0.63)	0.00
Number of lipid tests ordered												
...mean (sd)	0.59 (0.80)	0.69 (0.85)	-0.12	0.22 (0.62)	0.26 (0.68)	-0.06	0.59 (0.71)	0.70 (0.75)	-0.15	0.48 (0.69)	0.55 (0.73)	0.00
...median [IQR]	0.00 [0.00, 1.00]	1.00 [0.00, 1.00]	-1.21	0.00 [0.00, 0.00]	0.00 [0.00, 0.00]	0.00	0.00 [0.00, 1.00]	1.00 [0.00, 1.00]	-1.37	0.00 (0.77)	0.41 (0.81)	-0.01
Number of creatinine tests ordered												
...mean (sd)	0.06 (0.32)	0.07 (0.32)	-0.03	0.07 (0.41)	0.05 (0.27)	0.06	0.09 (0.38)	0.09 (0.37)	0.00	0.08 (0.38)	0.07 (0.34)	0.00
...median [IQR]	0.00 [0.00, 0.00]	0.00 [0.00, 0.00]	0.00	0.00 [0.00, 0.00]	0.00 [0.00, 0.00]	0.00	0.00 [0.00, 0.00]	0.00 [0.00, 0.00]	0.00	0.00 (0.44)	0.00 (0.36)	0.00
Number of BUN tests ordered												
...mean (sd)	0.03 (0.24)	0.05 (0.25)	-0.08	0.04 (0.31)	0.03 (0.23)	0.04	0.05 (0.29)	0.06 (0.28)	-0.04	0.05 (0.29)	0.05 (0.26)	0.00
...median [IQR]	0.00 [0.00, 0.00]	0.00 [0.00, 0.00]	0.00	0.00 [0.00, 0.00]	0.00 [0.00, 0.00]	0.00	0.00 [0.00, 0.00]	0.00 [0.00, 0.00]	0.00	0.00 (0.34)	0.00 (0.28)	0.00
Number of tests for microalbuminuria												
...mean (sd)	0.18 (0.61)	0.19 (0.64)	-0.02	0.06 (0.36)	0.08 (0.39)	-0.05	0.10 (0.37)	0.12 (0.39)	-0.05	0.10 (0.40)	0.11 (0.41)	0.00
...median [IQR]	0.00 [0.00, 0.00]	0.00 [0.00, 0.00]	0.00	0.00 [0.00, 0.00]	0.00 [0.00, 0.00]	0.00	0.00 [0.00, 0.00]	0.00 [0.00, 0.00]	0.00	0.00 (0.44)	0.00 (0.45)	0.00
Total N distinct ICD9/ICD10 diagnoses at the 3rd digit level Copy												
...mean (sd)	3.20 (4.99)	3.00 (5.09)	0.04	2.23 (5.06)	2.21 (4.86)	0.00	3.88 (6.40)	3.93 (6.39)	-0.01	3.32 (5.90)	3.27 (5.82)	0.00
...median [IQR]	0.00 [0.00, 5.00]	0.00 [0.00, 5.00]	0.00	0.00 [0.00, 2.00]	0.00 [0.00, 2.00]	0.00	0.00 [0.00, 6.00]	0.00 [0.00, 6.00]	0.00	0.00 (6.52)	0.00 (6.28)	0.00
For PS												
Hemorrhagic stroke+Other cerebrovascular disease+Cerebrovascular procedure (for PS); n (%)	392 (1.7%)	56 (1.9%)	-0.02	1,508 (2.2%)	344 (2.3%)	-0.01	2,242 (1.6%)	461 (1.8%)	-0.02	4142 (1.8%)	861 (2.0%)	-0.01
Occurrence of creatinine tests ordered (for PS); n (%)	1,003 (4.4%)	167 (5.7%)	-0.06	3,079 (4.5%)	535 (3.6%)	0.05	9,217 (6.8%)	1,813 (7.2%)	-0.02	13299 (5.9%)	2515 (5.8%)	0.00
Occurrence of BUN tests ordered (for PS); n (%)	611 (2.7%)	112 (3.8%)	-0.06	1,812 (2.7%)	365 (2.4%)	0.02	5,615 (4.1%)	1,169 (4.6%)	-0.02	8038 (3.5%)	1646 (3.8%)	-0.02
Occurrence of chronic renal insufficiency w/o CKD (for PS) v2; n (%)	0 (0.0%)	0 (0.0%)	#DIV/0!	0 (0.0%)	0 (0.0%)	#DIV/0!	0 (0.0%)	0 (0.0%)	#DIV/0!	0 (0.0%)	0 (0.0%)	#DIV/0!
Chronic kidney disease Stage 1-2 (for PS); n (%)	0 (0.0%)	0 (0.0%)	#DIV/0!	0 (0.0%)	0 (0.0%)	#DIV/0!	0 (0.0%)	0 (0.0%)	#DIV/0!	0 (0.0%)	0 (0.0%)	#DIV/0!
Chronic kidney disease Stage 3-6 (for PS); n (%)	0 (0.0%)	0 (0.0%)	#DIV/0!	0 (0.0%)	0 (0.0%)	#DIV/0!	0 (0.0%)	0 (0.0%)	#DIV/0!	0 (0.0%)	0 (0.0%)	#DIV/0!
Bladder stones+Kidney stones (for PS); n (%)	187 (0.8%)	36 (1.2%)	-0.04	861 (1.3%)	245 (1.6%)	-0.03	1,494 (1.1%)	311 (1.2%)	-0.01	2542 (1.1%)	592 (1.4%)	-0.03
Diabetes with peripheral circulatory disorders+Gangrene+Osteomyelitis(for PS) v3 with ICD10 Copy; n (%)	601 (2.7%)	51 (1.7%)	0.07	1,554 (2.3%)	285 (1.9%)	0.03	3,124 (2.3%)	485 (1.9%)	0.03	5279 (2.3%)	821 (1.9%)	0.03
Alcohol abuse or dependence+Drug abuse or dependence (for PS); n (%)	0 (0.0%)	0 (0.0%)	#DIV/0!	0 (0.0%)	0 (0.0%)	#DIV/0!	0 (0.0%)	0 (0.0%)	#DIV/0!	0 (0.0%)	0 (0.0%)	#DIV/0!
Diabetes with other ophthalmic manifestations+Retinal detachment, vitreous hemorrhage, vitrectomy+Retinal laser coagulation therapy (for PS); n (%)	86 (0.4%)	11 (0.4%)	0.00	937 (1.4%)	183 (1.2%)	0.02	1,247 (0.9%)	226 (0.9%)	0.00	2270 (1.0%)	420 (1.0%)	0.00
Other atherosclerosis+Cardiac conduction disorders+Other CVD (for PS) v2 Copy; n (%)	3,880 (17.1%)	540 (18.4%)	-0.03	21,635 (31.9%)	4,994 (33.5%)	-0.03	20,779 (15.3%)	4,065 (16.1%)	-0.02	46294 (20.4%)	9599 (22.3%)	-0.05
Previous cardiac procedure (CABG or PTCA or Stent) + History of CABG or PTCA (for PS) v3; n (%)	1,033 (4.6%)	148 (5.0%)	-0.02	3,026 (4.5%)	771 (5.2%)	-0.03	8,489 (6.2%)	2,092 (8.3%)	-0.08	12548 (5.5%)	3011 (7.0%)	-0.06
Hyperthyroidism + Hypothyroidism + Other disorders of thyroid gland (for PS); n (%)	3,831 (16.9%)	479 (16.3%)	0.02	8,436 (12.4%)	1,861 (12.5%)	0.00	17,662 (13.0%)	3,549 (14.1%)	-0.03	29929 (13.2%)	5889 (13.7%)	-0.01
Delirium + Psychosis (for PS); n (%)	198 (0.9%)	29 (1.0%)	-0.01	1,554 (2.3%)	211 (1.4%)	0.07	1,839 (1.4%)	311 (1.2%)	0.02	3591 (1.3%)	551 (1.3%)	0.03
Any use of Meglitinides (for PS); n (%)	38 (0.2%)	3 (0.1%)	0.03	324 (0.5%)	74 (0.5%)	0.00	377 (0.3%)	74 (0.3%)	0.00	739 (0.3%)	151 (0.4%)	-0.02
Any use of AGIs (for PS); n (%)	17 (0.1%)	4 (0.1%)	0.00	69 (0.1%)	28 (0.2%)	-0.03	109 (0.1%)	30 (0.1%)	0.00	195 (0.1%)	62 (0.1%)	0.00
CKD stage 3-6 + dialysis (for PS); n (%)	4 (0.0%)	0 (0.0%)	#DIV/0!	0 (0.0%)	0 (0.0%)	#DIV/0!	0 (0.0%)	0 (0.0%)	#DIV/0!	0 (0.0%)	#VALUE!	#VALUE!
Use of thiazide-United; n (%)	2,786 (12.3%)	342 (11.6%)	0.02	7,453 (11.0%)	1,623 (10.9%)	0.00	16,971 (12.5%)	3,212 (12.7%)	-0.01	27210 (12.0%)	5177 (12.0%)	0.00
Use of betablockers; n (%)	13,713 (60.5%)	1,820 (62.0%)	-0.03	44,683 (65.9%)	10,110 (67.7%)	-0.04	87,512 (64.3%)	16,625 (65.9%)	-0.03	145908 (66.3%)	28555 (66.3%)	-0.04
Use of calcium channel blockers; n (%)	7,737 (34.1%)	1,075 (36.6%)	-0.05	24,743 (36.5%)	5,699 (38.2%)	-0.04	48,655 (35.8%)	9,878 (39.2%)	-0.07	81135 (35.8%)	16652 (38.6%)	-0.06
All antidiabetic medications except Insulin; n (%)	4,109 (18.1%)	615 (20.9%)	-0.07	12,310 (18.2%)	2,931 (19.6%)	-0.04	25,209 (18.5%)	5,082 (20.1%)	-0.04	41628 (18.4%)	8628 (20.0%)	-0.04
DM Medications - Insulin Copy; n (%)	864 (3.8%)	128 (4.4%)	-0.03	3,888 (5.7%)	795 (5.3%)	0.02	5,129 (3.8%)	926 (3.7%)	0.01	9881 (4.4%)	1849 (4.3%)	0.00
Use of Low Intensity Statins; n (%)	8,138 (35.9%)	964 (32.8%)	0.07	23,820 (35.1%)	4,901 (32.8%)	0.05	48,921 (35.9%)	8,854 (35.1%)	0.02	80879 (35.7%)	14719 (34.2%)	0.03
Use of High Intensity Statins; n (%)	4,085 (18.0%)	619 (21.1%)	-0.08	13,552 (20.0%)	3,233 (21.7%)	-0.04	26,998 (19.2%)	5,459 (21.6%)	-0.06	43735 (19.3%)	9311 (21.6%)	-0.06
Malignant hypertension; n (%)	693 (3.1%)	107 (3.6%)	-0.03	27,053 (39.9%)	6,491 (43.5%)	-0.07	16,757 (12.3%)	4,133 (16.4%)	-0.12	44503 (19.6%)	10731 (24.9%)	-0.13
Cardiovascular stress test; n (%)	58 (0.3%)	13 (0.4%)	-0.02	449 (0.7%)	69 (0.5%)	0.03	579 (0.4%)	107 (0.4%)	0.00	1086 (0.5%)	189 (0.4%)	0.01
Echocardiogram; n (%)	3,464 (15.3%)	835 (28.4%)	-0.32	23,390 (34.5%)	7,438 (49.8%)	-0.31	29,798 (21.9%)	9,331 (37.0%)	-0.34	56652 (25.0%)	17604 (40.8%)	-0.34
Number of BNP tests												
...mean (sd)	0.08 (0.35)	0.09 (0.36)	-0.03	0.07 (0.40)	0.08 (0.35)	-0.03	0.11 (0.41)	0.13 (0.42)	-0.05	0.10 (0.40)	0.11 (0.39)	-0.03
...median [IQR]	0.00 [0.00, 0.00]	0.00 [0.00, 0.00]	0.00	0.00 [0.00, 0.00]	0.00 [0.00, 0.00]	0.00	0.00 [0.00, 0.00]	0.00 [0.00, 0.00]	0.00	0.00 (0.46)	0.00 (0.43)	0.00
Number of Cardiac biomarkers tests (tropnin, CK-MBs, Myoglobin, CPK)												
...mean (sd)	0.22 (0.91)	0.37 (1.23)	-0.14	0.21 (0.98)	0.32 (1.30)	-0.10	0.19 (0.49)	0.25 (0.56)	-0.11	0.20 (0.72)	0.28 (0.93)	0.00
...median [IQR]	0.00 [0.00, 0.00]	0.00 [0.00, 0.00]	0.00	0.00 [0.00, 0.00]	0.00 [0.00, 0.00]	0.00	0.00 [0.00, 0.00]	0.00 [0.00, 0.00]	0.00	0.00 (0.90)	0.00 (1.13)	0.00
Number of Ambulatory Blood pressure monitoring tests												
...mean (sd)	0.00 (0.03)	0.00 (0.03)	0.00	0.00 (0.04)	0.00 (0.04)	0.00	0.00 (0.02)	0.00 (0.04)	0.00	0.00 (0.03)	0.00 (0.04)	0.00
...median [IQR]	0.00 [0.00, 0.00]	0.00 [0.00, 0.00]	0.00	0.00 [0.00, 0.00]	0.00 [0.00, 0.00]	0.00	0.00 [0.00, 0.00]	0.00 [0.00, 0.00]	0.00	0.00 (0.04)	0.00 (0.04)	0.00
N of days on antihypertensive medications during baseline												
...mean (sd)	130.02 (68.95)	129.85 (66.94)	0.00	135.76 (65.79)	131.96 (67.63)	0.06	138.23 (64.13)	137.11 (64.13)	0.02	136.67 (65.13)	134.83 (65.56)	0.00
...median [IQR]	171.00 [89.00, 181.00]	168.00 [91.00, 181.00]	0.04	174.00 [110.00, 181.00]	171.00 [94.00, 181.00]	0.04	174.00 [122.00, 181.00]	173.00 [116.00, 181.00]	0.02	121.24 (74.47)	130.61 (73.42)	0.00
N of days in database anytime prior												
...mean (sd)	1,750.74 (1,238.00)	1,753.82 (1,191.57)	0.00	2,172.37 (1,246.30)	2,083.21 (1,203.95)	0.07	833.53 (537.51)	873.46 (457.48)	-0.08	1325.93 (889.77)	1352.52 (849.34)	0.00

